## 7.1 Discontinuation

For Cohort 1, subjects who discontinue the trial after the first dose will be asked, if they agree, to come for a last assessment (ET visit). Subjects who are discontinued for safety reasons may be asked to come for additional follow-up visits, at the investigator's discretion, after the ET visit to ensure appropriate medical care and AEs follow-up.

Subjects who discontinue will not be replaced.

Reasons for discontinuation include the following:

- The investigator decides that the subject should be withdrawn. If this decision is made because of an SAE, the IMP is to be discontinued in that subject immediately and appropriate measures are to be taken. The investigator will notify the sponsor immediately.
- If an application site reaction occurs, the investigator should use his or her best medical judgement as to whether to continue subject's treatment.
- The attending physician requests that the subject be withdrawn from the trial.
- The subject, for any reason, requires treatment with another therapeutic agent that has been demonstrated to be effective for treatment of the trial indication. In this case, discontinuation from the trial occurs immediately upon introduction of the new agent.
- The subject is lost to follow-up. In this case, a reasonable attempt to contact the subject and ascertain his or her status must be made, and these attempts must be documented.
- The subject becomes pregnant at any time during the trial.
- Other: the subject may withdraw from the trial for any other reason, including withdrawal of consent.
- The sponsor or regulatory authorities, for any reason, stop the trial. In this case, all subjects will be discontinued from the trial. The investigator will immediately, on discontinuance of the trial by the sponsor, in its entirety or at a clinical trial site, inform both the subjects and the research ethics board of the discontinuance, provide them with the reasons for the discontinuance and advise them in writing of any potential risks to the health of subjects or other persons.

## 7.2 Lost to Follow-Up

A subject will be considered lost to follow-up if he or she fails to return for scheduled visits and is unable to be contacted by the trial site staff.

The following actions must be taken if a subject fails to return to the clinic for a required trial visit:

- The site will attempt to contact the subject and reschedule the missed visit. The site will then counsel the subject on the importance of maintaining the assigned visit schedule and ascertain if the subject wishes to or should continue in the trial.
- Before a subject is deemed lost to follow-up, the investigator or designee will make every effort to regain contact with the subject (where possible, three telephone calls and, if necessary, a certified letter to the subject's last known mailing address or local equivalent methods). These contact attempts should be documented in the subject's medical record or trial file.
- If all attempts to contact the subject fail, he or she will be considered to have withdrawn from the trial with a primary reason of lost to follow-up.

## 8 TRIAL ASSESSMENTS AND PROCEDURES

### 8.1 Efficacy Assessments (Cohort 1 only)

Clinical evaluations of FFA will be performed by an experienced and qualified dermatologist (board certified or equivalent) or other suitably qualified and experienced designee. To assure consistency and reduce variability, the same assessor should perform all assessments on a given subject whenever possible.

#### 8.1.1 Lichen Planopilaris Activity Index

The LPPAI will be assessed at the visits specified in [Table 1](#). It is a quantitative measure of disease activity. The LPPAI records symptoms (pruritus, pain, burning), signs (erythema, perifollicular erythema and scale), a measure of activity (the anagen pull test), and spreading of the condition. These subjective and objective measures have been assigned a numeric value to establish a disease activity score. The weights given to the symptoms (30%), signs (30%), anagen pull test (25%), and presence of spreading (15%) led to the equation: LPPAI (0-10) = (pruritus + pain + burning)/3 + (scalp erythema + perifollicular erythema + perifollicular scale)/3 + 2.5 (pull test) + 1.5 (spreading/2). Symptoms and signs are recorded on a 4-point scale: 0 = absent (negative), 1 = mild (+/-), 2 = moderate (+), and 3 = severe (++/+++). The anagen pull test, when present, is a reliable measure of local disease activity. It involves taking hold of 10 to 20 hairs between the thumb, second and third fingers at the scalp end of the hair shafts, and pulling firmly away from the scalp with a perpendicular force to slide the fingers to the ends of the hair. The result is recorded both as a binary value (0 for no anagen hairs and 1 for the presence of anagen hairs) and as anagen hairs/total hairs pulled. Last is the assessment of disease extension, recorded as 0 (no spreading) versus 1 (indeterminate) versus 2 (spreading). When the hair loss is difficult to judge, the issue of extension is recorded as indeterminate. A detailed procedure of LPPAI score calculation is provided in [Appendix A](#).

#### 8.1.2 Frontal Fibrosing Alopecia Severity Score

The FFASS will be assessed at the visits specified in [Table 1](#). This index is based on the evaluation of the relevant clinical features in FFA. Those features are the grade of frontal and temporal hairline recession (from 1 to 5), grade of eyebrow loss (none, partial, or total), severity and extent of perifollicular erythema and hyperkeratosis, and severity and frequency of pruritus and pain associated with FFA. The resulting severity scores range from 0 to 25, with higher scores indicating greater FFA severity. The clinical features included in the FFASS are grouped into two categories: extent of alopecia (up to 21 points) and inflammation (up to 4 points). A detailed procedure of FFASS score calculation is provided in [Appendix B](#).

#### 8.1.3 Perifollicular Erythema and Scale

The perifollicular erythema and perifollicular scale of the selected lesional target area will be assessed visually at the visits specified in [Table 1](#). Each clinical finding (ie, perifollicular erythema and perifollicular scale) will be scored using the 4-point severity scale presented in [Table 6](#). To be eligible for this trial, subjects must have a lesional target area with a perifollicular erythema score  $\geq 2$  and a perifollicular scale score  $\geq 2$  at Screening and Day 1.

**Table 6: Perifollicular Erythema and Perifollicular Scale Severity Scale**

Score	Description
0	Absent/None
1	Mild
2	Moderate
3	Severe/Intense

#### **8.1.4 Pruritus Numerical Rating Scale**

The intensity of pruritus due to FFA will be recorded using a NRS. It will be assessed daily starting approximately 7 days prior to Day 1 and up to Day 8. Thereafter, it will be assessed only at the visits specified in [Table 1](#). This will be evaluated by asking subjects to assign a numerical score representing of the worst intensity over the last 24 hours of their symptoms on a scale from 0 to 10, with 0 indicating no symptoms and 10 indicating the worst imaginable symptoms. The NRS of pruritus is presented in [Appendix C](#).

#### **8.1.5 Burning Sensation Numerical Rating Scale**

The intensity of burning sensation due to FFA will be recorded using an NRS. It will be assessed daily starting approximately 7 days prior to Day 1 and up to Day 8. Thereafter, it will be assessed only at the visits specified in [Table 1](#). This will be evaluated by asking subjects to assign a numerical score representing of the worst intensity over the last 24 hours of their symptoms on a scale from 0 to 10, with 0 indicating no symptoms and 10 indicating the worst imaginable symptoms. The NRS of burning sensation is presented in [Appendix C](#).

#### **8.1.6 Pain Numerical Rating Scale**

The intensity of pain due to FFA will be recorded using an NRS. It will be assessed daily starting approximately 7 days prior to Day 1 and up to Day 8. Thereafter, it will be assessed only at the visits specified in [Table 1](#). This will be evaluated by asking subjects to assign a numerical score representing of the worst intensity over the last 24 hours of their symptoms on a scale from 0 to 10, with 0 indicating no symptoms and 10 indicating the worst imaginable symptoms. The NRS of pain is presented in [Appendix C](#).

#### **8.1.7 Hair Counts/Trichoscopy**

Hair counts/trichoscopy will be performed at the visits specified in [Table 1](#). Trichoscopy should be performed on the lesional target area, and should not overlap with the site of skin microbiome collection. Trichoscopy could overlap with the site of tape stripping or biopsy if needed, but should be performed first. The number of hairs, hair diameter, and hair density will be measured via fotofinder trichovision.

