### **8.3 Pharmacodynamic Assessments**

For subjects in Cohort 1, skin microbiome samples and skin biopsies will be collected in all subjects. Adhesive tape strip samples collection is optional and will be performed per investigator's judgement (based on available skin area on the scalp). However, every effort should be made to collect tape strip samples in all subjects.

For subjects in Cohort 1, it is preferred that the skin microbiome samples, tape strips (when applicable), and skin biopsies come from the same lesional target area. If needed, a second lesional

target area could be selected to allow for skin samples collection and the hair count/trichoscopy assessment. If two lesional target areas are selected, they should be of similar severity.

In addition, lesional skin biopsies should be as close as possible from the area of the skin tape stripping and preferably from the target area. Lesional skin tape strips could be collected from the same area where trichoscopy/hair counts is performed. Other assessments need to be done on different areas of the lesional target area(s) (ie, they should not overlap).

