### **8.3.1 Skin Biopsies**

The skin will be cleaned, disinfected, and anesthetized before skin biopsies are performed. Sterile gauze will be used to absorb any bleeding. The biopsy sites will be sutured if necessary.

Details about the collection, processing, handling, storage and shipping of biopsy samples will be provided in the laboratory manual.

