#### Cohort 1:

On Day 1, all subjects will have 2 skin biopsies (4-mm) collected prior to the first IMP application (1 from a lesional hair follicle within the target area and 1 from a non lesional hair follicle [eg, on the occipital scalp]). On Week 12, 1 skin biopsy (4-mm) will be collected from a hair follicle within the lesional target area (outside the scar of previous biopsies). Each biopsy will be split in half. One part will be used for IHC and the other part will be used for gene expression analysis.

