#### Cohort 1:

Adhesive tape strip collection is optional for subjects in Cohort 1 and will be collected per investigator's judgement (based on available skin area on the scalp). However, every effort should be made to collect tape strip samples in all subjects.

On Day 1, skin tape strips will be collected prior to the first IMP application from lesional skin and from nonlesional skin (eg, on the occipital scalp). On Week 12, skin tape strips will be collected at the same location of the lesional skin.

Lesional tape strip samples should ideally be collected in the lesional target area. However, if the lesional target area is not large enough to accommodate the tape stripping, tape strips can be collected adjacent/close to the target area. The tape strip area can be a combination of lesional and non lesional skin (or peri-lesional skin) on the scalp, as long as this area will be treated with the IMP. If possible, tape stripping should be performed on non-hair bearing skin.

Cohort 2:

On Day 1, skin tape strips will be collected on non-hair bearing healthy skin at a similar matched area of subjects with FFA (ie, on the forehead, as close as possible to the frontal scalp area).

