### **8.3.3 Skin Swabs for Microbiomes Analysis**

Collection of skin microbiome samples is a non-invasive procedure where a swab is passed along the skin. Skin swabs for microbiome analysis must be collected prior to the tape stripping and skin biopsies.

Details about the collection, handling, storage and shipping of microbiome samples will be provided in the laboratory manual.

Cohort 1:

On Day 1, skin swab for microbiome analysis will be collected for all subjects prior to the first IMP application (1 from the target area [lesional skin] and 1 from an uninvolved occipital scalp area). On Week 12, skin microbiome will be collected at the same location of the lesional skin of the target area.

Cohort 2:

Two skin swab samples for microbiome analysis will be collected on healthy skin at similar matched areas of subjects with FFA (ie, 1 on frontal scalp area and 1 from occipital scalp area).

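### Sections 8.1.7 and 8.3 conflict on whether the hair-count field may overlap a biopsy site, and doing trichoscopy first protects only the count made at that visit

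*Combined protocol and SAP*

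**What the plan says.** Section 8.1.7 sets the overlap rule for hair counts. It keeps trichoscopy away from the swab site, then adds: "Trichoscopy could overlap with the site of tape stripping or biopsy if needed, but should be performed first".

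Section 8.3 deals with the same space from the sampling side. It gives one allowance: "Lesional skin tape strips could be collected from the same area where trichoscopy/hair counts is performed". It continues: "Other assessments need to be done on different areas of the lesional target area(s) (ie, they should not overlap". Biopsies are discussed in the same paragraph and get no allowance; they are only to be near the tape-strip site: "lesional skin biopsies should be as close as possible from the area of the skin tape stripping and preferably from the target area". Sections 4.1 and 8.4.1 also name only tape strips as able to share the trichoscopy area.

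On timing, Table 1 puts hair counts at Day 1, Week 12, Week 24 and early termination (ET), and biopsies at Day 1 and Week 12. Section 8.3.1 takes one lesional 4-mm biopsy from the target area on Day 1. The Week 12 biopsy "will be collected from a hair follicle within the lesional target area (outside the scar of previous biopsies".

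On relocation, the other Week 12 lesional samples return to the same place. For swabs: "On Week 12, skin microbiome will be collected at the same location of the lesional skin of the target area". For tape strips: "On Week 12, skin tape strips will be collected at the same location of the lesional skin". Section 8.1.7 says only that trichoscopy is done on the lesional target area. The two tattoos in Section 8.4.1 mark that area, not a count field within it.

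**The concern.** There are two separate problems.

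First, a site following Section 8.3 would treat a biopsy inside the count field as not allowed, while a site following Section 8.1.7 could place one there. Neither section refers to the other.

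Second, the safeguard in Section 8.1.7 is order within a visit. The endpoint is a change across visits: Day 1 to Week 12 in the controlled period, and later visits against the same Day 1 baseline in the open-label extension (OLE, Section 9.3.3.2). A biopsy taken after today's count still comes before the next one. The protocol recognises scars as a problem for the Week 12 biopsy, which must avoid them, but sets no such rule for the Week 12 or Week 24 hair count.

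At stake is whether the change in hair number and density reflects the disease and its treatment, or partly reflects tissue removed by the trial's own procedures. Mean hair diameter need not change when part of a field is lost.

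**Working it through.** The plan states no figure on this point, so there is nothing to reproduce. The check compares the texts, follows the sequence of events, and does one area calculation for scale.

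**Step 1: the two rules.**
- Section 8.1.7: overlap with tape strips is allowed if needed; overlap with biopsy is allowed if needed; overlap with swabs is not.
- Section 8.3: tape strips may share the area; everything else is to be on different skin.

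They agree on tape strips and swabs and disagree on biopsies.

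**Step 2: sequence, if the overlapped field is counted again.**
- Day 1: count, then biopsy. The baseline field has no scar.
- Week 12: count, then biopsy. The count can include the Day 1 scar. An ET count before the Week 12 biopsy is in the same position.
- Week 24, or ET after Week 12: the count can include up to two scars, because the second biopsy avoids the first scar but nothing keeps it out of the count field.

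Section 1.3 already puts investigator assessments and photographs before skin sampling within a visit. The order rule in Section 8.1.7 therefore adds little, and nothing across visits.

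**Step 3: sequence, if a different field is counted.** An assessor may move away from the scar, since no section ties the count to a fixed field. The change from baseline then compares two different patches of skin.

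**Step 4: direction.** In the controlled period both arms have the same biopsies at the same visits, and randomization gives no reason for overlap to differ by arm. The expected effect is added variability, with some chance imbalance possible at about 15 subjects per arm. The OLE summary has no concurrent control, so a loss of counted skin could move hair number and density downward.

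**Step 5: scale.** Inputs: 4-mm punch (Section 8.3.1); target area about 3 cm × 6 cm (Section 8.4.1).
- One punch: π × 2² = 12.57 mm². Two punches: 25.13 mm².
- Target area: 30 × 60 = 1,800 mm² = 18 cm².
- Share of field = punch area ÷ field area.

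The documents do not give the count-field size. The rows marked assumed are illustration only and take each punch as lying wholly inside the field.

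| Field counted | One punch | Two punches |
|---|---|---|
| 18 cm² (whole target area) | 0.7% | 1.4% |
| 4 cm² (assumed) | 3.1% | 6.3% |
| 2 cm² (assumed) | 6.3% | 12.6% |
| 1 cm² (assumed) | 12.6% | 25.1% |

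Partial overlap and wound closure reduce these figures; on closure the plan says "The biopsy sites will be sutured if necessary". Area share is also not hair share, because nothing in the documents supports even hair density within a lesion.

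**The case against.** The best defence is that Section 8.3 is the general sampling rule and Section 8.1.7 the specific trichoscopy rule, with a limited exception for cases of need. The version history for version 2.0 lists both sections among those clarified on overlap, so the matter was considered. That is a fair reading, but no text says which section governs, so the conflict stands.

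The remaining objections limit the weight of the point, and they hold:
- The effect needs overlap to be used, the same field to be recounted, and the punch to take a material part of that field. The documents establish none of these.
- The only stated dimension gives 0.7% and 1.4%, although Section 8.4.1 accepts smaller target areas.
- Section 8.4.2 requires target-area photographs with constant magnification and settings, and Table 1 schedules them at the hair-count visits. They do not fix a count field, but may help to find it again.
- The study manual, or the separate statistical analysis plan announced in Section 9.3.1, may deal with this. Neither is in the text supplied, so it cannot be said that no handling exists.

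Aligning Section 8.3 with Section 8.1.7 would also end the contradiction. It would leave the scar inside the recounted field, so it solves only the first problem.

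A reader might infer that the treatment comparison is biased, or that counts will fall by a tenth or more. The documents support neither: biopsies are the same in both arms, and the larger percentages come only from assumed field sizes.

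**Conclusion.** The point holds at low severity. The conflict between Sections 8.1.7 and 8.3 on biopsy overlap is plain from the text and must be reconciled. It is equally plain that counting first protects only that visit's count.

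The consequence is conditional. With overlap and reuse of the field, a scar-free baseline is compared with a field holding one scar at Week 12 and up to two at Week 24 or at ET after Week 12. Without reuse, the comparison is not of like with like. Only the exploratory hair-count/trichoscopy endpoint is touched, through extra noise in the controlled period and a possible downward shift in the descriptive OLE summary.

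The size cannot be determined, because field size, frequency of overlap and reuse of the field are not stated. No group-level shift is claimed. A reader might also infer a threat to the main results; the primary gene-expression endpoint and the secondary adverse-event endpoint do not use hair counts and are unaffected.

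**What to change.** - Amend Section 8.1.7 to agree with Section 8.3 by removing the words that allow overlap with biopsy.
- On Day 1, locate the count field relative to the planned tattoos, with the Section 8.4.2 photographs as an aid. Reuse that field at Week 12, Week 24 and ET.
- Place lesional biopsies outside the field but within the target area, or in the already permitted second target area if space is short.
- Give the primary-endpoint biopsy priority. If overlap cannot be avoided, take the biopsy and record the overlap in the electronic case report form.
- In the separate analysis plan, add a sensitivity summary of hair counts without the overlapped fields.
- Do not classify overlap in advance as a major or non-major deviation. The per-protocol definition in Section 9.2 turns on major deviations that affect efficacy evaluations, so that judgement should follow the usual review.

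The cost is a two-word deletion, one instruction, one data item and one summary table. The downside is slightly less freedom in placing biopsies in small target areas. Where tape strips are taken inside the count field, the biopsy may sit a little further from them. Use of a second area also departs from the Section 8.3 preference for sampling a single target area.

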### 8.1.8 Hair Line Measurements

Hair line measurements will be performed at the visits specified in [Table 1](#). Lateral canthus (right and left) to hairline, lower glabellar crease to hair line, top of frontalis muscle to hair line, and mid brow to hair line (right and left) will be measured using a disposable paper ruler.

## 8.2 Safety Assessments

### 8.2.1 Vital Signs

The following vital signs will be recorded at the visits specified in [Table 1](#) (Cohort 1) and [Table 2](#) (Cohort 2) with the subject in a seated position, after having sat calmly for at least 5 minutes: systolic and diastolic blood pressure (mmHg), pulse (bpm), and body temperature (°C).

Weight (kg) and height (cm) will be collected at the screening visit. Weight (kg) will also be collected at other visits specified in [Table 1](#) (Cohort 1) and [Table 2](#) (Cohort 2).

If deemed appropriate by the investigator, clinically significant findings in the vital signs will exclude a subject from trial participation. For Cohort 1 only, any abnormal finding related to vital signs that the investigator considers to be clinically significant must be recorded as an AE.

### 8.2.2 Complete Physical Examination

For subjects in Cohort 1 only, the following sites/systems will at least be included in the complete physical examination, which will be performed at the visits specified in [Table 1](#):

- General appearance
- Dermatological (except FFA)
- Head, eyes, ears, nose, throat (HEENT)
- Respiratory
- Cardiovascular
- Abdominal
- Neurological
- Musculoskeletal
- Lymphatic

Information for all physical examinations must be included in the source document. If deemed appropriate by the investigator, clinically significant findings in the physical examination will exclude a subject from trial participation. Any significant change will be reported as an AE in the source document and eCRF.

